## 6.4 PROCEDURES FOR DISCONTINUATION

### 6.4.1 Patient Discontinuation

The patient is not obliged to give his or her reasons for withdrawing prematurely from the trial. However, a reasonable effort will be made to ascertain the reason, while fully respecting the patient's rights. If he or she is unwilling or unable to complete of the final study visit he or she will be invited to report safety and efficacy endpoints either in the eCRF or by phone. Special consideration will be given to collect remaining medication and pill boxes. If the withdrawal is exclusively related to the trial drug therapy, this will be classified as a violation of the protocol and the data collection will be continued as specified in 6.2.4 and 6.2.5. Patient discontinuation will be monitored by checking the eCRF at day 2 and at the telephone follow-up at day 5 ( $\pm 1$ ).

### 6.4.2 Trial Discontinuation

The whole trial may be discontinued at the discretion of the PI or the sponsor in the event of any of the following:

- Occurrence of AEs unknown to date in respect of their nature, severity and duration
- Medical or ethical reasons affecting the continued performance of the trial
- Difficulties in the recruitment of patients
- Cancellation of drug development

The sponsor and principal investigator will inform all investigators, the The Norwegian Medicines Agency and REK (the Norwegian Regional Ethics Committee South East) of the termination of the trial along with the reasons for such action. If the study is terminated early on grounds of safety, the The Norwegian Medicines Agency and REK will be informed within 15 days.

## 6.5 ASSESSMENT OF EFFICACY

Patients will be encouraged to record outcomes at the same time of day during the treatment period.

### 6.5.1 Leg pain

A NRS of average pain intensity in the previous 24 hours will be used. The 0–10 NRS has been recommended as a core outcome measure in trials of chronic pain [33] and has excellent psychometric properties, usability and compliance. It will be solicited by a presentation of the numbers from 0 to 10, with 0 meaning “No pain” and 10 meaning “Pain as bad as you can imagine.” The use of a single pain item is supported by the IMMPACT recommendations for assessing pain in clinical trials [33]. Baseline pain will be determined by the average of the two recordings at day 0 (at the clinic and at home in the evening).

### 6.5.2 Back pain

24 h average back pain will be assessed by a 0-10 NRS as described above.

### 6.5.3 Disability

The Roland Morris Disability Questionnaire modified for use in sciatica (RMDQ-S) will be used. The RMDQ [70] is one of the most commonly used measures of back pain related activity limitation [71]. The RMDQ-S [72] is a modification inquiring explicitly about both back and leg pain, including 23 questions that can be answered by yes (=1) or no (=0). The RMDQ-S has measurement properties comparable to the original RMDQ [73] and has been used in previous sciatica studies [74-76]. The MIC of the RMDQ-S is approximately 4 points [73].

### 6.5.4 Sciatica symptoms

Symptoms will be assessed by The Sciatica Bothersomeness Index (SBI) which is comprised of four sciatica symptoms: 1) leg pain, 2) numbness or tingling in leg, foot, or groin, 3) weakness in leg/foot, and 4) back or leg pain while sitting.

Each symptom is rated 0-6 and a total score is obtained by summing up the ratings across the four symptoms. We have previously validated the SBI [77] and it has been used as outcome in other large sciatica studies [75, 78].

### 6.5.5 Drug intake

The patients will record the number of tablets (IMP and Paracetamol) taken each day. Additionally, “Sykehusapoteket” will count the remaining IMP and Paracetamol tablets returned and record the difference from the number handed out at baseline [79]. The patients will also record the use of other pain medication by medication name and dosage on a daily basis.

### 6.5.6 Global perceived change (GPC)

Global perceived effect will be measured on a verbal rating scale as response to the question: “You joined this study five (resp. ten) days ago. How is your sciatica/back problem now compared to then? Tick one alternative: Completely gone, much better, better, a little better, no change, a little worse, worse and much worse”.

### 6.5.7 Work/study status

Current work or study status will be assessed by self-report: (i) at present I am able to work or study as usual, (ii) at present I am unable to work or study as usual, (iii) other (specify)

## 6.6 TOLERABILITY ASSESSMENTS

Tolerability will be monitored by laboratory tests and patient's reports of adverse events. At baseline and at the end of treatment the following tests will be performed:

- Complete blood count (hemoglobin, hematocrit, leucocytes, thrombocytes)
- Creatinin, estimated glomerular filtration rate (eGFR)

- Liver function tests (aspartate transaminase (ASAT), alanine transaminase (ALAT), alkaline phosphatase (ALP)

The monitoring of adverse events is described below, see chapter 7.

## **6.7 PROTOCOL ADHERENCE ASSESSMENTS**

Protocol adherence will be assessed by (i) examining the patients' reports in the e-CRF (at day 2) and (ii) a follow-up conducted by telephone (at day 5 ±1). At day 2 we will examine whether IMP intake, rescue medication intake, questionnaire completion and adverse events were reported. At the day 5 (±1) follow-up the same issues will be examined and any problems will be discussed with the patient. Minor divergence from the protocol will be classified as a not important (minor) deviation while one that severely affects the quality of data or impacts subjects' safety will be classified as an important (major) protocol violation.

## **6.8 END OF TRIAL**

The end of this trial will be the last visit of the last subject. The Norwegian Medicines Agency will be notified within 90 days after end of trial.

# **7 SAFETY MONITORING AND REPORTING**

The investigator is responsible for the detection and documentation of events meeting the criteria and definition of an adverse event (AE) or serious adverse event (SAE). Each patient will be instructed to contact the investigator immediately should they manifest any signs or symptoms they perceive as serious.

## **7.1 DEFINITIONS**

### **7.1.1 Adverse Event (AE)**

An AE is any untoward medical occurrence in a patient administered a pharmaceutical product and which does not necessarily have a causal relationship with this treatment. An AE can therefore be any unfavorable and unintended sign (including an abnormal laboratory finding), symptom, or disease temporally associated with the use of a medicinal (investigational) product, whether or not related to the medicinal (investigational) product. The term AE is used to include both serious and non-serious AEs.

### **7.1.2 Non-serious AEs**

Since the AE profile of Naproxen is well established, non-serious AEs will be recorded, but not reported to the Norwegian Medicines Agency. The same goes for Paracetamol. The eCRF will include a daily checklist including expected non-serious AEs (see section 7.2) as well as space to specify other unpleasant events.

### **7.1.3 Serious Adverse Event (SAE)**

A SAE is defined as any untoward medical occurrence that at any dose:

- Results in death
- Is immediately life-threatening
- Requires in-patient hospitalization or prolongation of existing hospitalization
- Results in persistent or significant disability or incapacity
- Is a congenital abnormality or birth defect
- Is an important medical event that may jeopardize the subject or may require medical intervention to prevent one of the outcomes listed above.

### **7.1.4 Suspected Unexpected Serious Adverse Reaction (SUSAR)**

Suspected Unexpected Serious Adverse Reaction (SUSAR) is defined as an adverse reaction that is both unexpected (not consistent with the applicable product information as defined in section 7.2) and also meets the definition of a Serious Adverse Reaction (SAE, see section 7.1.3). There may be a causal link to the administered product, known as a Serious Adverse Reaction (SAR). There must be a certain degree of probability that the event is harmful, and an undesirable, reaction to the medicinal product in the study, regardless of the administered dosage.

## **7.2 EXPECTED ADVERSE EVENTS**

Expected AEs according to the Summary of Product Characteristics (SPC) for Naproxen will be recorded in the eCRF. Expected AEs in *italics* will be included in a tick-off list in the eCRF.

### **7.2.1 Expected non-serious AEs related to Naproxen**

- Dyspepsia
- Nausea
- Diarrhea
- Vomiting
- Abdominal pain
- Skin eruption
- Tinnitus
- Headache
- Tiredness
- Dizziness

### **7.2.2 Expected non-serious AEs related to Paracetamol**

- None

## **7.3 TIME PERIOD FOR REPORTING AE AND SAE**

In this study, participation implies daily recording of patient reported outcomes. Concurrently patients will be asked to report any potential AEs on a daily basis. Additionally, at the follow up at 5 ( $\pm 1$ ) and at the final study visit we will inquire about AEs. During the course of the study all SAEs will be proactively followed up for each patient; events will be followed up to resolution, unless the event is considered by the investigator to be unlikely to resolve due to the underlying disease. Every effort will be made to obtain a resolution for all SAEs, even if the events continue after discontinuation/study completion.

## **7.4 RECORDING OF ADVERSE EVENTS**

### **7.4.1 Non-serious AEs**

Patients may record non-serious AEs on a tick off list including 10 events expected for Naproxen, see section 7.2.1. Additionally, patients may report other non-serious AEs in their own words. At the follow-up at 5 ( $\pm 1$ ) at the final study visit the investigator will record whether the event is resolved or still ongoing and whether any action was taken.

### **7.4.2 Serious AE**

The investigator will record the following information in the CRF:

The nature of the event(s) will be described by the investigator in precise standard medical terminology (i.e. not necessarily the exact words used by the patient).

The duration of the event will be described in terms of event onset date and event ended date.

The intensity of the adverse event will be classified as Mild / Moderate / Severe; according to Common Terminology Criteria for Adverse Events version 4.0 (CTCAE).

The Causal relationship of the event to the study medication will be assessed as one of the following:

- Unrelated. There is not a temporal relationship to investigational product administration (too early, or late, or investigational product not taken), or there is a reasonable causal relationship between non-investigational product, concurrent disease, or circumstance and the AE.
- Unlikely. There is a temporal relationship to investigational product administration, but there is not a reasonable causal relationship between the investigational product and the AE.
- Possible. There is reasonable causal relationship between the investigational product and the AE. Dechallenge information is lacking or unclear.
- Probable. There is a reasonable causal relationship between the investigational product and the AE. The event responds to dechallenge. Rechallenge is not required.
- Definite. There is a reasonable causal relationship between the investigational product and the AE.

Action taken: The outcome of the adverse event – whether the event is resolved or still ongoing.

## **7.5 REPORTING PROCEDURE**

### **7.5.1 AEs and SAEs**

All adverse events and serious adverse events that should be reported as defined in section 7.1.1 will be recorded in the patient's CRF.

SAEs will be reported by the investigator to the sponsor, [name], Forskningsavdelingen, Sykehuset Østfold, Tel [name]; [contact]; E-mail: [contact], within 24 hours after the site has gained knowledge of the SAE. Every SAE will be documented by the investigator on the SAE pages in the CRF. The SAE Report Form will be completed, signed and sent to sponsor. The initial report will promptly be followed by detailed, written reports if necessary. The initial and follow-up reports will identify the trial subjects by unique code numbers assigned to the latter.

The sponsor will keep detailed records of all SAEs reported by the investigators and performs an evaluation with respect to seriousness, causality and expectedness.

### **7.5.2 SUSARs**

SUSARs will be reported to the The Norwegian Medicines Agency and REK according to national regulation. The following timelines will be followed:

The sponsor will ensure that all relevant information about suspected serious unexpected adverse reactions that are fatal or life-threatening is recorded and reported as soon as possible to the Norwegian Medicines Agency and REK in any case no later than seven (7) days after knowledge by the sponsor of such a case, and that relevant follow-up information is subsequently communicated within an additional eight (8) days.

All other suspected serious unexpected adverse reactions will be reported to the The Norwegian Medicines Agency and to REK as soon as possible but within a maximum of fifteen (15) days of first knowledge by the sponsor. SUSARs will be reported using the CIOMS form.

### **7.5.3 Annual Safety Report**

Once a year throughout the clinical trial, the sponsor will provide the Norwegian Medicines Agency with an annual safety report DSUR.

### **7.5.4 Clinical Study Report**

The adverse events and serious adverse events occurring during the study will be discussed in the safety evaluation part of the Clinical Study Report.

## **7.6 PROCEDURES IN CASE OF EMERGENCY**

The principle investigator will assure that there are procedures and expertise available to cope with emergencies during the study. All patients will at inclusion receive a card with contact information about the sponsor and local investigator, as well as emergency contact information. In the event of an SAE, the Investigator may only break the treatment code if the appropriate future management of the patient necessitates knowledge of the current treatment.

# **8 DATA MANAGEMENT AND MONITORING**

## **8.1 CASE REPORT FORMS (CRF)**

### **8.1.1 Electronic case report forms (eCRFs)**

Patients and designated investigator staff will enter the data required by the protocol into the eCRF. A web-based eCRF software solution, Viedoc™ and ViedocMe™ (Uppsala, Sweden) will be used. ViedocMe™ lets patients report data through their phone, PC or tablets. Viedoc is approved for use in clinical trials by Oslo University Hospital and is supported by the Norwegian Clinical Research Infrastructures Network (NorCRIN). In order to maximize data quality study participants will receive daily reminders via sms text messages at an agreed time. If any assessments are omitted the eCRF program will send automatic reminders with a copy to the study coordinator. The coordinator will be of help to solve practical problems and encourage the patients to complete the study forms. In case the patient is unable to log into the eCRF or the web site is unavailable, the study coordinator may enter data obtained by a telephone or personal interview. Viedoc will enable identification of patient data recorded by a coordinator. After database lock, electronic copies of the subject data will be archived at the investigational site.

### **8.1.2 CRF paper back-up**

All patients will receive a paper CRF which can be used if the eCRF is unavailable. In such cases, the paper CRF will be source data and a study collaborator will enter the data into the eCRF.

## **8.2 SOURCE DATA**

The following points will be described in the medical records of each patient:

- That the patient is participating in the study, e.g. by including the enrollment number and the study code
- Date when Informed Consent was obtained from the patient
- Results of all assessments confirming a patient's eligibility for the study
- Diseases (past and current; both the disease studied and others, as relevant)
- Results of assessments performed during the study
- Visits to the clinic / telephone contacts during the study, including those for study purposes only
- Serious Adverse Events (if any) including causality assessments
- Date of, and reason for, discontinuation from study treatment
- Date of, and reason for, withdrawal from study
- Date of death and cause of death, if available

Patient reported outcome (PRO) measures will not be recorded in the electronic patient journal system but directly into the eCRF and the eCRF will be source data. If they are recorded on paper and then entered into the eCRF, then the paper CRF is source data. Results of laboratory tests will be entered by a study collaborator and the patient journal will be source data. Results of clinical findings will be entered directly into the eCRF.

## **8.3 STUDY MONITORING**

Department of Clinical Research Support, Oslo University Hospital, will be appointed to monitor this study. The study monitor will visit the center(s) regularly checking the following:

- Reporting of adverse events and all other safety data
- Adherence to protocol
- Maintenance of required regulatory documents
- Study Supply accountability
- Facilities and equipments
- Data completion on the eCRFs including source data verification.

The monitor will review the relevant eCRFs for accuracy and completeness and will ask the site staff to adjust any discrepancies as required. Monitoring of data completion will be performed within the eCRF solution. When the study monitor has verified the CRFs, the data will be locked for further handling and statistical evaluation. The monitor will be allowed access to source data for source data verification in which case a review of those parts of the hospital records relevant to the study may be required.

## **8.4 CONFIDENTIALITY**

The investigator will arrange for the secure retention of the patient identification and the code list. The PI will store a hard copy list including all participants in locked cabinets at Sykehuset Østfold. The PI and one of the co-investigators will have access to the code list.

## **8.5 DATABASE MANAGEMENT**

During the study eCRF-data will be retained at Viedoc. After locking, the data file will be imported into a designated database at Sykehuset Østfold. All information concerning the study, including the Site File, will be stored for 15 years at Sykehuset Østfold, inaccessible to unauthorized personnel. Data management will be under the guidance of Department of Clinical Research Support, Oslo University Hospital.

# **9 STATISTICAL METHODS AND DATA ANALYSIS**

## **9.1 DETERMINATION OF SAMPLE SIZE**

The sample size calculation is based on a mean difference between the Naproxen group and the placebo group of 1.5 (0-10) at ten days with a SD of 2.5 using a two-sample t test. There is no robust evidence for the smallest worthwhile

between group pain relieving effect in sciatica. In previous sciatica studies sample size were calculated based on between group differences of 1.5 and 1.0 [80, 81]. In a recent RCT of pregabalin the sample size was calculated based on a between group difference of 1.5 [36]. In knee osteoarthritis, a condition in which NSAIDs are generally recommended, the treatment effect of NSAIDs is about 1.0 [82-84]. The estimated SD of 2,5 is based on a recent Cochrane review of NSAID studies in sciatica [30].

Assuming 90% power and a two-tailed 5% significance level a sample size of 60 subjects is needed in each treatment arm. Allowing for a combined dropout and non-compliance rate  $\leq 20\%$  [85] the total number of subjects will be 150.

## 9.2 RANDOMIZATION

### 9.2.1 Allocation- procedure to randomize a patient

Trial participants will be assigned to NSAID or placebo based on a simple (unrestricted), 1:1, randomization approach. Stratifying by center will be performed by block randomization. Viedoc™ will establish a computer-generated allocation sequence list which will be used by Kragerø Tablettproduksjon AS to number the study medicines. The allocation list will be concealed for all other study personell and patients. A copy of the allocation list will be stored by the Department of Clinical Research Support, Oslo University Hospital.

### 9.2.2 Blinding and emergency unblinding

Patients, investigators, pharmacists and data analyst will be blinded to treatment allocation. Un-blinding of the treatment allocation is permissible only if the safety and well-being of the patient is being compromised. The decision to reveal the treatment allocation during the study may only be done by the Principal Investigator. A copy of the allocation list will be stored by Klinisk forskningsstøtte OUS who will be responsible for unblinding during business hours. Additionally, the Principal Investigator ([name]) can be contacted 24/7 on telephone ([contact] for unblinding.

The date and time of un-blinding will be documented in the eCRF and in the patient's hospital records. In the event of an SAE, the Investigator will only break the treatment code if the appropriate future management of the patient necessitates knowledge of the current treatment.

### 9.2.3 Assessment of patient blinding

At the end of treatment (day 10), or at withdrawal, patients will be asked to guess what treatment they have received. The response categories will include (i) Naproxen, (ii) placebo and (iii) don't know. Descriptive data (2x3 table) will be presented, no statistical analyses will be performed [86].

## 9.3 POPULATION FOR ANALYSIS

The following populations will be considered for the analyses:

- Intention to treat (ITT) population: All randomized participants, regardless of protocol adherence.
- Safety population: Includes all subjects who have received at least one dose of study medication. Subjects who withdraw from the study will be included in the safety analysis. A list of withdrawn subjects, with the reasons for withdrawal, will be generated.

## 9.4 PLANNED ANALYSES

Deviation from the original statistical plan will be described and justified in the Clinical Study Report.

### 9.4.1 Blinded analyses

To minimize the chance of misleading interpretations of the study results, data will be analyzed blinded to the randomization codes [87]. Depending on treatment group, the randomizer will provide each of the participants with a code, A or B, leaving the investigators uncertain if A or B represents Naproxen or placebo. Before unblinding, a summary of data interpretation assuming that treatment A is Naproxen, and assuming treatment B is Naproxen, will be prepared.

## 9.5 STATISTICAL ANALYSIS

### 9.5.1 Statistical methodology

The primary analyses will be performed by linear mixed effects models for repeated measures (MMRM) [88]. Mean changes from baseline will be analyzed using a restricted maximum likelihood (REML) based repeated measures approach. Analyses will include the categorical effects of treatment and treatment-by-visit interaction as fixed covariates and intercept as a random variable. Additionally, responder analyses comparing the percentage of patients who have

improved according to predefined cut-offs in the two groups (see 2.2), will be performed using a  $\chi^2$  test [89]. The strategy for dealing with missing values will be decided during the blind review of the data at the end of the trial. A statistical analysis plan will be prepared and made accessible at clinicaltrials.gov.

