### 2.3 PRIMARY ENDPOINT

- The change in leg pain (24 hours average) rated on a 0-10 numeric rating scale (NRS) from baseline to day 10 based on longitudinal analyses of daily observations.

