27.1 Analysis of the primary outcome

The primary objective of the NIS trial is to estimate and test treatment differences in leg pain intensity at 10 days after commencement of Naproxen or placebo. Multiple measurements taken on the same patient will be correlated. This is accounted for in the analysis by a mixed effects model; either a linear mixed model (LMM) or a generalized linear mixed model (GLMM) depending on the distribution of the leg pain intensity. The model includes fixed effects for treatment, time (11 time points), the treatment-by-time interaction, and baseline measurements of leg pain plus age and gender. The primary result will be the treatment effect estimates over the period of treatment with 95% CI.

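### SAP 27.1 does not fix the within-patient covariance of the primary model and uses day 0 as both outcome and covariate, so the standard error of the primary test is left open and may be wrong

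*Protocol*

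**What the plan says.** SAP 27.1 deals with repeated measurements in general terms: "Multiple measurements taken on the same patient will be correlated. This is accounted for in the analysis by a mixed effects model". The model may be linear or generalized linear. The section then lists only "fixed effects for treatment, time (11 time points), the treatment-by-time interaction, and baseline measurements of leg pain plus age and gender". It names no patient-level random effect, residual covariance or fallback if the fit fails. SAP 27.3 speaks of centres as further random effects, and SAP 27.4 of bootstrapping random effects; neither defines the patient-level ones. The sensitivity analyses in SAP 27.5 vary the population, the imputation and the covariates, but not the covariance.

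Protocol 9.5.1 is the only place that states a structure: "Analyses will include the categorical effects of treatment and treatment-by-visit interaction as fixed covariates and intercept as a random variable". The same section uses the label MMRM and says: "Mean changes from baseline will be analyzed using a restricted maximum likelihood (REML) based repeated measures approach".

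On the time points, SAP section 15 has leg pain measured daily from day 0 to day 10, which makes 11. For RMDQ-S and SBI it lists days 0, 5 and 10, which matches the three time points of SAP 27.2.

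On the contrast, SAP 27.1 opens by aiming to "estimate and test treatment differences in leg pain intensity at 10 days after commencement of Naproxen or placebo" and ends: "The primary result will be the treatment effect estimates over the period of treatment with 95% CI". Protocol 2.3 defines the endpoint as a change "from baseline to day 10 based on longitudinal analyses of daily observations". Protocol 9.1 and SAP section 11 size the trial on a difference of 1.5 at day 10.

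**The concern.** A random intercept with independent residuals assumes the same variance on every day and the same correlation between any two days. Daily pain scores need not behave like that. Scores on adjacent days are usually closer than scores ten days apart. Once the model conditions on baseline, or uses change from baseline, the residual variance then grows with distance from day 0. Day 10, the day on which the trial is sized, is the furthest away.

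A standard error that is too small puts the false-positive rate of the primary test above 5%; one that is too large loses power. Because the covariance is not written down, two analysts who both follow the SAP could report different primary p-values. The double use of day 0 adds a second error. Under a random intercept it biases the standard error downwards even in conditions where that structure would otherwise be correct.

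**Working it through.** **The plan's own figure.** Difference 1.5, SD 2.5, two-sided 5%, 90% power (protocol 9.1, SAP 11). A two-sample t test has power 0.898 with 59 per arm and 0.903 with 60, so 60 per arm; 120/0.8 = 150. The sample size reproduces and is not in question. The day-10 SE it implies is 2.5 × √(2/60) = 0.456.

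**Formula at day 10.** With complete data and a full treatment-by-time model, a random-intercept REML fit gives every day the mean of the daily residual variances. So model SE / true SE = √(mean daily residual variance / day-10 residual variance), and type I error = 2Φ(−1.96 × ratio).

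**Worked example (assumed: SD 2.5 every day, correlation 0.90 per day of separation, days 1-10 as outcomes, one baseline term).** The common baseline slope is β = mean of 0.9^k over k = 1 to 10 = 0.586. The residual variance on day k is 6.25 × (1 − 2β·0.9^k + β²).
- Day 1: SD 1.34. Day 10: SD 2.42.
- Mean over days: 6.25 × (1 − β²) = 4.10, SD 2.03.
- Model SE 2.03 × √(2/60) = 0.370; true SE 2.42 × √(2/60) = 0.441.
- Ratio 0.84; type I error 10.1%.

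**Opposite direction (assumed: no baseline adjustment, SD falling from 3.0 to 2.5).** The model SE is 0.503 against a true 0.456: ratio 1.10, type I error 3.1%, power 0.87 instead of 0.91.

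**Range.** There are nine decaying correlation structures: 0.80, 0.90 or 0.95 per day, or a stable share of 0.4 or 0.6 plus a part decaying at 0.3, 0.5 or 0.8 per day. They are crossed with five SD paths: flat 2.5; rising 2.0 or 1.5 to 2.5; falling 2.5 to 2.0 or 1.5. That gives 45 scenarios. Day-10 type I error under a random intercept:

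| Model | Flat SD | Rising SD | Falling SD | Below 5% |
|---|---|---|---|---|
| Days 1-10, one baseline term | 5.3-12.1% | 7.7-17.3% | 1.2-9.6% | 12 of 45 |
| Change from baseline, no baseline term (protocol 9.5.1) | 5.5 to about 13% | 7.0-17.2% | 4.2-12.2% | 5 of 45 |
| Days 0-10 plus baseline term (SAP 27.1) | 6.1-13.9% | 8.8-19.3% | 1.5-11.3% | 10 of 45 |

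Under compound symmetry with constant SD, the first two models give exactly 5.0%.

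**Day 0 on both sides.** Take compound symmetry with correlation 0.5 and unit variance, so that a random intercept is the true structure. With 11 outcomes, β = (1 + 10 × 0.5)/11 = 0.545.
- Residual variance: day 0, (1 − β)² = 0.207; every other day, 1 − 2β(0.5) + β² = 0.752; mean 0.702.
- Day 10: √(0.702/0.752) = 0.966, type I error 5.8%. For correlations 0.2 to 0.8 the range is about 5.5-6.0%.
- Average over days 1-10, true variance: 0.55 − 0.545 + 0.298 = 0.302.
- Average over days 1-10, model: the mean between-day covariance is (20 × (−0.0207) + 90 × 0.2521)/110 = 0.202, so the variance is 0.202 + (0.702 − 0.202)/10 = 0.252.
- Ratio √(0.252/0.302) = 0.91, type I error about 7%.

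The ratio for this average is 0.909-0.916 in all 45 scenarios. In the two models without day 0 as an outcome it is 1.00.

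**Simulation with dropout.** 75 per arm, 18-20% monotone dropout, five assumed scenarios, days 1-10 as outcomes. The random intercept gave type I errors of 10.7, 0.7, 12.1, 15.7 and 11.1% (700 replicates each). An unstructured covariance with Kenward-Roger gave 4.1-5.4% (2,000 replicates each).

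**The case against.** The strongest reply is that the SAP governs and chooses no wrong covariance; it is silent. It already departs from protocol 9.5.1 by adding baseline, age and gender and by allowing a generalized model. MMRM often means an unstructured covariance, and the protocol does not itself state independent, equal-variance residuals. This stands in part. A reader might infer that the SAP prescribes a random-intercept analysis, and the documents do not support that. What remains is the omission: neither document says unstructured, and the section carrying the MMRM label also specifies the random intercept.

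A reader might also infer that this trial's false-positive rate is inflated. That is not shown. Every SD path and correlation above is assumed, the results fall on both sides of 5%, and the figures are illustrations only.

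A third objection is that SAP 27.1 calls the primary result an effect over the treatment period, for which a random intercept would be harmless. With complete data that is true only when day 0 is not an outcome. Under SAP 27.1 as written the averaged effect is affected too. This rests on counting the 11 time points as days 0-10, as SAP section 15 does. Days 1-10 plus the end-of-study visit would also make 11, but section 15 does not describe the primary outcome that way.

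SAP 27.4 allows other models, and the analysis uses A/B codes. Neither names a covariance, and a two-sided p-value is the same whichever code is naproxen, so coding does not replace pre-specification.

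**Conclusion.** The concern holds as a gap in pre-specification, together with a model-form error. The gap is certain: SAP 27.1 names no within-patient covariance, and the only stated structure is the protocol's random intercept. Its effect on this trial is unknown in direction and size. If the random intercept is used with independent residuals, day-10 type I error could plausibly lie anywhere from about 1% to 19% across the assumed scenarios and model forms. It is more often above 5% than below, and exactly 5.0% if variances and correlations are constant and day 0 is not an outcome.

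The double use of day 0 is a smaller but more predictable fault. Under a random intercept it makes the SE of the averaged effect about 9% too small, and it does not need decaying correlations to do harm. The sample size of 150 is unaffected. The point should be settled before unblinding; it does not show that the planned analysis is invalid.

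**What to change.** In SAP 27.1, before unblinding:

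1. Use days 1-10 as outcomes and day 0 as covariate only. Do the same for back pain, and use days 5 and 10 for RMDQ-S and SBI.
2. For the linear mixed model, replace the random intercept with an unstructured within-patient covariance fitted by REML. If it does not converge, use heterogeneous Toeplitz, then heterogeneous AR(1), each with robust standard errors. In simulation these fallbacks gave 4.1-5.0% with robust errors but 3.9-7.6% with model-based ones. A small-sample method such as Kenward-Roger is optional, since it moved type I error by at most 0.25 points.
3. State that this supersedes the random intercept in protocol 9.5.1.

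As a separate point, name the day-10 difference as the primary contrast, to match protocol 2.3, protocol 9.1 and SAP 11, and report the effect over the period as supportive. If the generalized model remains an option, its patient-level random effects need their own sentence; the checks here cover the linear model only.

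The cost is SAP wording. Protocol 9.4 already provides for deviations to be justified in the study report. All 20,000 simulated unstructured fits converged, but with purpose-written REML code, so other software may behave differently. The day-10 SE may be larger than under a random intercept (0.464 against 0.348 with flat SD and correlation 0.90 per day) or smaller (0.252 against 0.323 with falling SD). Simulated power for 1.5 at day 10 was at least 89.3%.
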